### 3.3 Sample Size Determination

The target number of subjects to be randomized per cohort is 30 individuals seronegative for SARS-CoV-2 Spike IgG antibodies (20 subjects to the RD-X19 treatment arm and 10 subjects for Sham control), for a minimum total of 60 subjects. At the sponsors option, the total number of subjects can be increased by an additional 150 total subjects to include all serostatuses after a dose has been selected based on adequate safety/tolerability observed for the final dose cohort.

Based on findings in the EB-P12-01, the hazard ratio observed for the time to sustained symptom resolution in that early feasibility trial was HR=0.4 between active RD-X19 and Sham.

The increased sample size in the Final Cohort (up to 180 total), with an anticipated roughly equal number of antibody positive to negative individuals enrolled during the option, will lead to approximately 90 seropositive and 90 seronegative subjects. The modified Full Analysis Set (mFAS) population containing only antibody negative subjects (as defined in Section 4, 60 RD-X19: 30 Sham) has at least 90% power to detect meaningful changes in SARS-CoV-2 symptom resolution from baseline (Hazard ratio of 0.4) for the first primary endpoint. These power calculations assume that testing will be carried out using  $\alpha = 0.025$  one-sided, up to a 20% dropout rate due to discontinuations or hospitalizations, as well as an assumption that the proportions of subjects having the event (for the first primary endpoint) by Day 14 is 85% for the RD-X19 arm and 75% for the Sham arm.

In the Full Analysis Set (FAS) for the Final Cohort, the primary analysis population including all randomized subjects receiving at least one treatment, the increased sample size (increase by a minimum of 100 RD-X19: 50 Sham) has at least 90% power to detect a Hazard ratio of 0.5 between RD-X19 and Sham for the first primary endpoint. These power calculations assume that testing will be carried out using  $\alpha = 0.025$  one-sided, as well as an assumption that the proportions of subjects having the event (for the first primary endpoint) by Day 14 is 90% for the RD-X19 arm and 85% for the Sham arm, with adjustment for multiple endpoints as described in Section 5.1.1.

Note: The two primary endpoints will be tested using a maximum experimentwise type 1 error of 0.025 1-sided and using a maximum experimentwise type 1 error of 0.050 1-sided. In section 5.1.1, under the procedure for multiple endpoint adjustment, the significance levels for testing each of the two individual primary endpoints are derived so that the maximum experimentwise type 1 error is 0.025 one-sided, and significance levels are also derived so that the maximum experimentwise type 1 error is 0.050 one-sided.

## 4 Populations To Be Analyzed

Three subject populations are defined as follows:

- (1) Safety/Full Analysis Set (FAS): This population will include all randomized subjects who receive at least 1 study treatment. This Population will be used for all analysis of safety data, and is also the primary analysis population for efficacy. Subjects will be analyzed based on actual treatment received.
- (2) Modified Full Analysis Set (mFAS): This population will include all randomized subjects who received at least one treatment and who tested negative for SARS-CoV-2 antibodies at baseline. Subjects will be analyzed based on actual treatment received.
- (3) Per-Protocol Population (PP): This population will include all randomized subjects in the FAS population who complete the study and did not have a major protocol deviation (MPD). The PP population will be used for supportive analysis of the clinical and virological endpoints. MPDs are those that could have interfered with the administration of treatment or the precise evaluation of treatment efficacy.

MPDs may include but will not be limited to the following:

- Violation of inclusion/exclusion criteria
- Use of prohibited concomitant medications during the treatment period
- Missed Visit 4 (Day 8) or Visit 4 outside of window
- Did not complete 100% (6 out of 6) of scheduled doses in the first 3 days, or at least 75% (11 out of 14), regardless of the time of enrollment on Day 1
- Returned for Day 14 Visit outside the designated visit window

All MPDs will be identified and documented in the Protocol Violation and Protocol Deviation Log before the database lock and study unblinding for analysis.

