8.5 Device Discontinuation

8.5.1 Study Pausing Criteria

If observations of an SAE or patterns of discrete or non-resolving device-related TEAEs grade 2 or higher in the same SOC PT are observed in a single subject, dosing will be discontinued for that subject and observed at regulatory scheduled follow up visits.

EB-P20-01 enrollment in any Cohort will be paused if any of the following events occur:

- Any subject experiences a device related SAE.
- Any subject experiences laryngospasm, bronchospasm or anaphylaxis within 2 hours after treatment.
- Two (2) or more subjects experience an allergic reaction such as generalized urticaria (defined as occurring at three or more body parts) within 72 hours after treatment.
 - Potential photoallergy or phototoxicity to one or more photosensitizing drugs in the subject's medical history should be investigated in all cases.

See “Medications that Increase Sensitivity to Light: A 1990 Listing (Levine 1990).”

- Three (3) or more subjects experience a Grade 2 or higher TEAE (including local, systemic and/or clinical laboratory abnormalities), in the same SOC grouping of Preferred Terms based on the Medical Dictionary for Regulatory Activities (MedDRA) coding, considered to be related to RD-X19.

While the study is paused, attribution will be determined and assigned and the SMC will be notified that a consultation is required. Given the frequency of visits and the duration of the protocol, study device use may continue in unaffected subjects within a cohort until a recommendation is provided to unpause or terminate cohort enrollment by the SMC.

The SMC, when convened by the sponsor, will not only make a recommendation to unpause enrollment or discontinue dosing in a given cohort, but will also make a recommendation to the sponsor for ascending, or descending from Cohort A in the event safety/tolerability signals are observed with the first 24 J/cm² RD-X19 device.

A study volunteer may elect to discontinue participation in the trial at any time. Investigative staff will ask the volunteer to return for an early termination evaluation, but they are under no obligation to do so. All study subjects must return the RD-X19 device at study termination and study staff must verify that the device serial number matches the study subject to whom it was assigned.

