 - Subjects will be instructed to fill out diary cards twice daily to assess their symptoms associated with disease progression and record the number of treatments completed. Each of the eight symptoms will be rated on a 4-point scale from none (0) to severe (3). Temperature and oxygen saturation will also be measured and recorded via devices provided by site personnel and taken home by the subject. Subjects will also be asked if they experience any shortness of breath. Reminders will be sent to each subject twice daily via an appropriate communication platform (e.g. text messaging) and up to date diary cards should be presented at each clinical visit to be eligible for subject payments. Between visits on Days 2 and 4, to enhance safety monitoring and reinforce adherence to at-home study procedures, each subject will be contacted via phone and verbally go through diary procedures and document any AEs.
- Severe COVID-19 Clinical Outcomes
 - There is a small amount of risk that subjects with mild-to-moderate COVID-19 may have an unknown health problem or co-morbidity at the time of screening that can lead to rapid worsening of condition or hospitalization during study. Worsening of condition will be characterized by study subjects who experience COVID-19 progression defined by an increase of the composite COVID-19 severity score greater than baseline at any point in the study on or after day 3.

- Medically attended visits as a result of severe COVID-19 clinical outcomes will be aggregated into the following categories:
 - 1) those who require medical attention attributed to COVID-19;
 - 2) those who progress to severe disease with respiratory rate >30/minute and/or O2 saturation ≤93% on room air or FiO2 ≥300% with any respiratory distress;
 - 3) those who require hospitalization for severe COVID-19;
 - 4) those who require endotracheal ventilation or ECMO with or without the use of solumedrol; and
 - 5) those who die.
- Subjects with a primary care, urgent care, or emergency room visit that are not hospitalized as a result of their medical consultation, may continue treatment with the investigational device and should attend regularly scheduled follow up visits per protocol. Subjects that are admitted to the hospital should discontinue all treatment in lieu of standard of care for severe/critical COVID-19 illness.

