#### 5.5.1 Analysis of Primary Efficacy Endpoint

The primary analysis for each of the two primary endpoints will be the comparison via an unstratified log-rank test between the RD-X19 treatment arm and sham from the Final Cohort and is based on the FAS population. This analysis will be supplemented with a graphical display and medians derived by the Kaplan Meier method.

All time-to-event analyses will be measured starting from the time of randomization. The data handling rules as described in Section 5.2.1 will be applied before analyses of the primary efficacy endpoints. These data handling rules cover cases related to subjects discontinuing the study early due to hospitalization for COVID-19, and cases related to subjects discontinuing the study early due to other reasons. Subjects that did not discontinue early but who did not achieve sustained resolution will be censored at the date of their Visit 5.

The Kaplan-Meier derived medians will be presented from the FAS population for the Final Cohort together with 95% CIs using the Brookmeyer & Crowley (1982) method and will include values for the RD-X19 treatment arm and the Sham arm. 25th and 75th percentiles will also be provided together with their 95% CIs using this same method.

Cox proportional hazards regression models (with a single term for treatment) will be employed to analyze the primary efficacy endpoints to derive a hazard ratio in each case between the RD-X19 treatment arm and the sham arm from the Final Cohort and will be based on the FAS population. Two-sided 95% confidence intervals and two-sided 90% confidence intervals will also be derived for the hazard ratios from the above models.

In addition, to evaluate the potential impact of subject baseline characteristics to the treatment effect estimation, the Cox proportional hazards regression will be performed for the Final Cohort based on the FAS population adjusting for the following set of covariates:

- 1) the COVID-19 Composite Severity Score at baseline defined as the sum of the eight individual COVID-19 signs and symptoms severity scores divided by eight (grouping of <1.25,  $\geq 1.25$ )
- 2) baseline disease status of mild vs. moderate disease (subjects meeting entry criteria are considered to be mild unless the physical/vital signs examination documents clinical signs suggestive of moderate illness)  
All subjects are designated as Mild with the exception of subjects:

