	-- n (%) subjects who require hospitalization for severe COVID-19	XX (XX.X)	XX (XX.X)	XX (XX.X)	XX (XX.X)
	-- n (%) subjects who require endotracheal ventilation or ECMO	XX (XX.X)	XX (XX.X)	XX (XX.X)	XX (XX.X)
	-- n (%) subjects who die	XX (XX.X)	XX (XX.X)	XX (XX.X)	XX (XX.X)
Modified Full Analysis Set					
	N	XX	XX	XX	XX
	n (%) Subjects who experience progression of COVID-19 	XX (XX.X)	XX (XX.X)	XX (XX.X)	XX (XX.X)
	n (%) Subjects with severe clinical outcomes (at least one of following)	XX (XX.X)	XX (XX.X)	XX (XX.X)	XX (XX.X)
	-- n (%) subjects who require medical attention or intervention attributed to COVID-19	XX (XX.X)	XX (XX.X)	XX (XX.X)	XX (XX.X)
	-- n (%) subjects who progress to severe disease 	XX (XX.X)	XX (XX.X)	XX (XX.X)	XX (XX.X)
	-- n (%) subjects who require hospitalization for severe COVID-19	XX (XX.X)	XX (XX.X)	XX (XX.X)	XX (XX.X)
	-- n (%) subjects who require endotracheal ventilation or ECMO	XX (XX.X)	XX (XX.X)	XX (XX.X)	XX (XX.X)
	-- n (%) subjects who die	XX (XX.X)	XX (XX.X)	XX (XX.X)	XX (XX.X)
Per Protocol Population					
	N	XX	XX	XX	XX
	n (%) Subjects who experience progression of COVID-19 	XX (XX.X)	XX (XX.X)	XX (XX.X)	XX (XX.X)
	n (%) Subjects with severe clinical outcomes (at least one of following)	XX (XX.X)	XX (XX.X)	XX (XX.X)	XX (XX.X)
	-- n (%) subjects who require medical attention or intervention attributed to COVID-19	XX (XX.X)	XX (XX.X)	XX (XX.X)	XX (XX.X)
	-- n (%) subjects who progress to severe disease 	XX (XX.X)	XX (XX.X)	XX (XX.X)	XX (XX.X)
	-- n (%) subjects who require hospitalization for severe COVID-19	XX (XX.X)	XX (XX.X)	XX (XX.X)	XX (XX.X)
	-- n (%) subjects who require endotracheal ventilation or ECMO	XX (XX.X)	XX (XX.X)	XX (XX.X)	XX (XX.X)
	-- n (%) subjects who die	XX (XX.X)	XX (XX.X)	XX (XX.X)	XX (XX.X)

[1]: Progression of COVID-19 is defined by increase of composite COVID-19 severity score (> baseline score) at any point in the study on or after Day 3.

[2]: Subjects will be designated as Severe having any one of the following: Respiratory Rate  $\geq 30$ , Heart Rate  $\geq 125$ , SpO2  $\leq 93\%$ , or lung infiltrates upon imaging  $>50\%$ .

EmitBio Inc.  
Protocol: EB-P20-01  
SAP Version: 2.0

Source: Listing 16.x.x  
O:\Studies\EmitBio\EB-P20-01\Biometrics\Programs\Tables\xxx.sas ran on Month Day, Year at hh:mm on data from Month Day, Year.

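### Per Protocol membership depends partly on outcome: study completion is undefined, COVID-19 hospitalisation and death get no exception, and the PP death row is zero by construction for deaths before the Day 14 visit (minor)

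*SAP*

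**What the plan says.** SAP section 4 gives the PP definition as "This population will include all randomized subjects in the FAS population who complete the study and did not have a major protocol deviation (MPD", and Protocol 10.3 sets the same two conditions. The SAP's open-ended list of possible major deviations includes "Missed Visit 4 (Day 8) or Visit 4 outside of window" and a dose rule: "Did not complete 100% (6 out of 6) of scheduled doses in the first 3 days, or at least 75% (11 out of 14". Protocol 10.3 states without qualification that failing the dose thresholds is a major deviation. Neither document defines study completion.

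Protocol 9.2 directs that "Subjects that are admitted to the hospital should discontinue all treatment in lieu of standard of care". Protocol 8.5.1 provides, for a subject with an SAE or a pattern of device-related TEAEs of grade 2 or higher, that "dosing will be discontinued for that subject", with follow-up visits continuing. Protocol 8.5.4 adds that stopping the device is not stopping the study.

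SAP 5.2.1 makes subjects hospitalised for COVID-19 treatment failures censored at 384 hours. SAP 5.5.1 describes that rule as covering "subjects discontinuing the study early due to hospitalization for COVID-19", and SAP 3.3 counts hospitalisations within its dropout allowance for the mFAS. The footnotes to Tables 14.2.1.1 to 14.2.1.4, which contain PP blocks, repeat the 384-hour rule. Table 14.2.2.3 prints the row "n (%) subjects who require hospitalization for severe COVID-19", with ventilation and death rows, for FAS, mFAS and PP alike.

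**The concern.** A subject who is hospitalised or dies has reached a failure outcome of the trial. If that event also removes the subject from PP, membership is decided partly by the outcome under study rather than by adherence. Two outputs suffer. The PP hazard ratio would be presented as support for the FAS result while being insensitive to a difference between arms in hospitalisation. The PP block of Table 14.2.2.3 would show no deaths before the Day 14 visit, and few or no hospitalisations or ventilations, whatever happened in the trial. A reader could take those zeros as a finding.

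**Working it through.** **1. The plan's dose figure.** 0.75 × 14 = 10.5, rounded up to 11, and 11/14 = 78.6%. The stated 11 of 14 reproduces. At two doses a day, dose 11 is the first dose of Day 6.

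**2. Doses taken when the device is stopped, with none missed before.** A stop before dosing on Day 4 gives 6 doses, Day 5 gives 8, Day 6 gives 10, Day 7 gives 12 and Day 8 gives 14.
- If both thresholds must be met (6 of 6 in the first three days and at least 11 of 14), any stop before dose 11 fails.
- If meeting either is enough, which the wording also allows, only a stop before the six doses of Days 1 to 3 are complete fails.

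**3. Who is in PP.**
- Death before the Day 14 visit: the subject cannot complete the study on any reading, so is always excluded. The PP death row is zero for these deaths.
- Admission before dose 11: excluded on dose count if both thresholds apply. Neither document provides an exemption.
- Visit 4 missed, or outside Days 7 to 9, because of admission: a listed possible major deviation.
- Admission that ends study participation: excluded as a non-completer, in line with SAP 5.5.1.
- At least 11 doses, Visit 4 in window, admitted and discharged, Visit 5 by Day 16 (14 + 2): meets every listed criterion if Protocol 8.5.4 governs, and stays in PP as a 384-hour failure.

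The documents settle the first case. The others turn on an undefined term, an ambiguous conjunction and an open-ended list.

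**4. Illustration of what removal does.** The documents give no hospitalisation rates, so all rates below are assumed. Setting: 116 RD-X19 and 58 sham (the 174 subjects of the SAP 5.1.1 example, split 2:1), exponential times, 85% of sham resolved by Day 14 (SAP 3.3), 2,000 simulated trials. The hazard ratio among non-hospitalised subjects is assumed to be 1.5; it is in neither document. It lies between the 2.0 obtained by inverting the SAP's 0.5 and the 1.21 implied by 90% against 85% resolved under exponential times: ln(0.10)/ln(0.15) = 2.303/1.897 = 1.21. Hospitalised subjects are held as failures at 384 hours in the full set and all removed from PP. Values above 1 favour RD-X19, because the event is resolution.

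| Hospitalised, RD-X19 / sham | HR, full set | HR, PP |
|---|---|---|
| 1% / 3% | 1.54 | 1.50 |
| 2% / 6% | 1.59 | 1.50 |
| 3% / 10% | 1.67 | 1.50 |
| 3% / 3% | 1.45 | 1.50 |
| 6% / 2% | 1.30 | 1.50 |
| 10% / 3% | 1.19 | 1.50 |

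Expected hospitalised subjects: 116 × 0.01 + 58 × 0.03 = 2.9 in the first row and 116 × 0.10 + 58 × 0.03 = 13.3 in the last.

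A second setting has 120:60, 90% resolved by Day 14 and no effect among non-hospitalised subjects (1,500 trials). Full set against PP: 1.00 and 1.00 at 5%/5%; 0.93 and 1.01 at 5%/2%; 0.85 and 1.01 at 10%/3%.

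In both settings the PP value stays where the non-hospitalised subjects put it, whether the device lowers or raises hospitalisation.

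**The case against.** The strongest reply is that nothing decisive rests on PP. Hypothesis testing is on the Final Cohort in the FAS, where hospitalised subjects stay in as failures. Severe outcomes are also tabulated for FAS and mFAS, and safety uses the FAS. Restricting PP to completers with adequate exposure is conventional. This stands, and it sets the severity.

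Second, a reader might infer that every stop the protocol directs leads to exclusion and that all hospitalised failures vanish from PP. The documents do not support that. Protocol 8.5.1 and 8.5.4 keep subjects who stop the device in follow-up, and the last case in step 3 can remain. SAP 5.5.1 refers to subjects who leave because of hospitalisation; it does not say that every hospitalised subject leaves. Protocol 11.1.8 defines a deviation as non-compliance, and stopping on admission is compliance, although Protocol 10.3 still counts the missed doses as a major deviation.

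Third, a reader might infer that the exclusions remove device-intolerant subjects mainly from the active arm. The documents give no intolerance rate for this trial. Protocol 4.1 reports no device-related TEAEs in the earlier sham-controlled study, and events under sham can also be attributed to the device.

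Fourth, the simulation removes every hospitalised subject by assumption, and the large shifts need high rates. The earlier study, with 31 subjects, reported no medical intervention beyond over-the-counter remedies and no discontinuations. It is too small to fix a rate, but it does not point to 10%. The table therefore shows direction and an upper limit for PP's insensitivity, not an expected bias.

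**Conclusion.** The point holds in limited form. PP selection depends partly on outcome because study completion is undefined, hospitalisation and death get no exception, and Protocol 8.5.4 and SAP 5.5.1 point in different directions. Only the death row is certain: it is zero for any death before the Day 14 visit. How many hospitalised failures leave PP depends on when they are admitted, how the dose rule is read and what completion means. If all leave, a full-set hazard ratio of 1.54 to 1.67 (fewer hospitalisations on RD-X19) or 1.19 to 1.30 (more on RD-X19) becomes 1.50 in PP, under the assumed rates and assumed hazard ratio. No planned figure is wrong, and FAS and mFAS results do not change. Severity is minor: a supportive analysis and one table block.

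**What to change.** In SAP section 4, and in Protocol 10.3 at the next amendment:
- Define study completion, and reconcile Protocol 8.5.4 with SAP 5.5.1 on whether a hospitalised subject has left the study.
- State whether both dose thresholds must be met or either one.
- State that non-completion, or visits and doses missed, because of COVID-19 hospitalisation or death does not by itself exclude a subject from PP, and that such subjects keep the 384-hour failure rule.

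If the third item is not adopted, report the hospitalisation, ventilation and death rows of Table 14.2.2.3 for FAS and mFAS only, and remove the 384-hour footnote from the PP blocks of Tables 14.2.1.1 to 14.2.1.4.

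The cost is a few sentences in the SAP. The protocol wording needs IRB approval, so it can wait for an amendment made for other reasons. The downside is that PP will contain a few subjects with fewer than 11 doses. How tolerability stops under Protocol 8.5.1 count for PP is a trade-off between exposure and selection, and is left to the sponsor to state.

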## 5 Planned Analyses

All study data will be presented in by-subject data listings. Tabulations will be displayed separately for RD-X19 and Sham from the Final cohort for the primary analysis, and, RD-X19

from each cohort individually, Pooled RD-X19 from both Cohorts and Pooled Sham from both Cohorts for supportive/secondary analyses.

## 5.1 Methodological Considerations

### General Conventions

SAS software (version 9.4 or higher) will be used for all data analyses and tabulations.

Data for all investigational centers will be pooled for analysis. The sham groups from different cohorts will not be combined for the analyses unless otherwise specified. For all analyses, subjects will be analyzed based on actual treatment received.

Unless specified elsewhere, baseline is defined as the last available measurement prior to administration of study treatment. Change from baseline will be calculated as the post-baseline value minus the baseline value.

Summary tables will include the data based upon the protocol scheduled time points. For subjects who are early discontinued from the study or have visits outside of the allowed window, all efficacy assessments captured at the visit will be assigned to the protocol scheduled time point as follows:

Visit of Treatment Period	Range for ET / Visit Re-allocation*
Visit 2 / Day 3	Study Day 1 to 3
Visit 3 / Day 5 ( $\pm$ 1 day)	Study Day 4 to 6
Visit 4 / Day 8 ( $\pm$ 1 day)	Study Day 7 to 9
Visit 5 / Day 14 ( $\pm$ 2 day)	Study Day $\geq$ 10

\*Study day = date of visit - date of first treatment + 1

Descriptive statistics of continuous variables will include n, mean, standard deviation (SD), median, and range. Generally, the minimum and maximum values will be presented to the same decimal precision as the raw values, the mean and median values to one additional decimal, and the SD, to two more decimal places than the raw values. Summaries for categorical data will include frequencies and percentages. Percentages will be presented to one decimal place.

